Study Protocol

Title: Prevalence of Carotid Web in Youth Assessed by Duplex Sonography: a Cross-Sectional Study

Short Title: Carotid Web in Youth

Acronym: CaWY Study

ID: G25-498516

Version: 1.4

Date: October 20, 2025

Authors: [name] [name], M.D., Ph.D.

[name]., Ph.D.

[name]., Ph.D.

Affiliation: Center for Health Research, Faculty of Medicine, University of Ostrava, Ostrava, Czech Republic

1) Background and Rationale

A carotid web (CaW) is a shelf-like, thin, triangular endoluminal projection—typically arising from the posterior wall of the internal carotid artery (ICA) bulb—considered by many to be an intimal variant of fibromuscular dysplasia and associated with embolic ischemic stroke in otherwise low-risk, younger patients. Although CT angiography (CTA) is most frequently used to diagnose CaW, characteristic appearances are detectable by carotid duplex ultrasound (DUS) on longitudinal B-mode with supportive Doppler findings; microflow/superb microvascular imaging can improve conspicuity. Population prevalence in the general young adult population is unknown; most estimates come from stroke cohorts ($\approx 2\%$ among symptomatic populations; higher within cryptogenic stroke subsets), so a dedicated, population-based sonographic study is needed.

2) Objectives and Hypotheses

Primary objective: Estimate point prevalence of carotid web in a general young adult population aged 15–25 years using duplex sonography.

Secondary objectives:

- Describe CaW laterality and morphology (web thickness, length, and projection angle) on ultrasound.
- Estimate prevalence of concomitant ICA/CCA atherosclerotic change or stenosis.
- Assess inter-observer agreement for CaW detection on DUS.
- In an adjudicated subset, compare DUS-suspected CaW with CTA (optional validation).

Hypothesis: Carotid web is present in 2 % of the general 15–25-year population (two-sided).

(This is a planning assumption; true prevalence may be lower/higher. Literature in symptomatic cohorts ranges roughly 2%, higher in cryptogenic stroke; general-population data are lacking.)

3) Study Design

Cross-sectional, multi-center, population-based sonographic survey with blinded central image adjudication, reported per STROBE guidelines for cross-sectional studies.

4) Study Population

Inclusion criteria

- Age 15 – 25 years at enrollment.
- Able to provide informed consent.

Exclusion criteria (for primary analysis; still recorded if present):

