- **Vascular risk factors:** smoking status, BP at visit, lipid profile if available, personal history of stroke/TIA/migraine, OCP use (females), recreational drugs, connective tissue disease/FMD history.
- **Ultrasound fields:** laterality; CaW category (absent/possible/probable), web dimensions (length, thickness, projection angle—estimate), distance from flow divider, presence of superimposed thrombus, plaque descriptors, standard velocities (CCA, bulb, ICA), ICA/CCA PSV ratio, EDV.
- **Imaging quality scores** and reasons for non-diagnostic studies.

10) Validation Substudy

- Participants with definite or possible CaW on DUS plus 1:2 matched DUS-negative controls (matched by age/sex/site) will invited for CTA within 4 weeks to evaluate concordance (index test: DUS; reference standard: CTA with thin-slice oblique sagittal reconstructions). Outcome: sensitivity/specificity and positive predictive value of DUS criteria. (CTA descriptions of CaW as thin, shelf-like posterior bulb defects guide the reference call.)

11) Outcomes

- **Primary:** Point prevalence of **probable CaW** (participants with ≥ 1 carotid web / all with diagnostic scans), with 95% CI adjusted for sampling design.
- **Secondary:**
 - Prevalence including **possible + probable** (sensitivity analysis).
 - Distribution by side (left/right/bilateral).
 - Association between CaW and sex, smoking, BP, OCP use (exploratory).
 - Inter-observer agreement metrics.
 - In validation substudy: DUS diagnostic accuracy vs CTA.

12) Statistical Analysis Plan

- **Weighting:** Apply sampling weights for cluster/strata to estimate population prevalence; robust SEs (Taylor linearization) or survey-design GLMs.
- **Descriptives:** Means/SDs or medians/IQRs; counts/% with 95% CIs.
- **Primary analysis:** Weighted prevalence and **exact (Clopper–Pearson) or Wilson** CIs for rare events; compare strata with Rao–Scott χ^2 .
- **Regression (exploratory):** Survey-weighted Poisson (log link, robust variance) for prevalence ratios of CaW vs candidate covariates.
- **Reliability:** Cohen’s κ with 95% CI (categorical), ICC(2,1) for continuous measures.
- **Missing data:** Report flow; use complete-case for primary prevalence; multiple imputation for covariate analyses if $>5\%$ missing.

- **Sensitivity analyses:** (i) include **possible** CaW as positive; (ii) restrict to scans with top quality scores; (iii) per-reader estimates.

13) Bias Minimization & Quality Control

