- Pre-specified imaging protocol; machine presets harmonized across sites.
- Central training and periodic re-calibration; quarterly site audits of randomly selected studies.
- Consecutive sampling within clusters to reduce selection bias; track response rates.
- Maintain blinding; lock image sets before adjudication.

14) Ethics and Safety

- Minimal-risk imaging study; no ionizing radiation in the primary protocol.
- Informed consent; separate consent for optional CTA.
- Participants with **incidental significant carotid stenosis** or suspected thrombus receive counseling and referral per local care pathways.
- Data privacy per GDPR; coded IDs; secure storage.

15) Feasibility & Timeline

- **July-December 2025:** Finalize SOPs, train sonographers, pilot 50 scans to confirm criteria and quality metrics.
- **January 2026 – June 2026:** Enrollment and scanning.
- **May – June 2026:** Central reads and adjudication.
- **July – December 2026:** Analysis, manuscript preparation.

16) Case Report Forms (CRFs) — Core Fields (summary)

- **CRF-1 (Eligibility & Consent).**
- **CRF-2 (Demographics/Risk).**
- **CRF-3 (Ultrasound Acquisition):** device, probe, settings, windows obtained, quality.

- **CRF-4 (Ultrasound Findings):** CaW category; measurements; Doppler velocities; plaque; stenosis category; images saved (IDs).
- **CRF-5 (Adjudication):** reader A/B calls; consensus; κ .
- **CRF-6 (Validation Substudy):** CTA done (Y/N), CTA result (CaW Y/N), discordance reason.

17) Reporting

- Report per **STROBE**; include gallery of representative DUS images (longitudinal shelf-like lesion, transverse membrane, microflow swirl) and a flow diagram. Explicitly discuss limitations: web detection is operator-dependent; ultrasound criteria are less standardized than CTA; very low prevalence may limit precision without large samples.

Key References (for protocol justification)

1. **Fontaine L, et al.** *Ultrasound characteristics of carotid web*. J Neuroimaging. 2022. Describes B-mode/Doppler appearances; microflow imaging improves detection. ([PMC](#), [PubMed](#))
2. **Chen H, et al.** *Carotid webs: pathophysiology, diagnostic approaches, and management*. J NeuroIntervent Surg. 2024. Overview; ultrasound visualization best in longitudinal B-mode. ([jn.is.bmj.com](#))
3. **Radiopaedia (review).** *Carotid web*. Emphasizes shelf-like defect at posterior ICA bulb and CTA reference standard. ([Radiopaedia](#))

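### The CTA substudy samples on the ultrasound result, so it can estimate predictive values but not the sensitivity, nor without weighting the specificity, that Section 10 names as outcomes

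*Protocol*

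**What the plan says.** Section 10 of the protocol sets the selection rule: "Participants with definite or possible CaW on DUS plus 1:2 matched DUS-negative controls (matched by age/sex/site) will invited for CTA within 4 weeks". The comparison is "index test: DUS; reference standard: CTA with thin-slice oblique sagittal reconstructions", and the section closes with "Outcome: sensitivity/specificity and positive predictive value of DUS criteria". Section 11 repeats the aim among the secondary outcomes: "In validation substudy: DUS diagnostic accuracy vs CTA". Section 2 lists it as an optional secondary objective, and Section 14 requires a separate consent for CTA.

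The only weighting described in Section 12 is in the instruction "Apply sampling weights for cluster/strata to estimate population prevalence". Nothing is said about the fraction of DUS-negatives sent to CTA. The protocol also does not say that the accuracy figures will be unweighted.

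The primary outcome in Section 11 is the prevalence of probable CaW. The invitation in Section 10 names the definite and possible categories and leaves out probable.

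**The concern.** Verification by the reference standard depends on the index test. DUS-positives are invited, while only a small, fixed multiple of them is drawn from the DUS-negatives. Quantities conditional on the DUS result (PPV, and NPV with a qualification about matching) can be estimated from such a sample. Quantities conditional on true disease status (sensitivity and specificity) cannot, because the mix of positives and negatives in the table is set by the 1:2 rule and not by the population.

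Most missed webs lie among the DUS-negatives who never have CTA. A raw table would therefore make ultrasound appear to miss almost nothing. It would also understate specificity, because true negatives are sampled sparsely while false positives are not. At stake are a secondary accuracy result that readers may use to judge ultrasound as a screening tool, and CTA in DUS-negative young people done partly for an estimate that the design cannot deliver. The mismatch of categories adds a second problem: read literally, the PPV would not refer to the group counted in the primary outcome.

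**Working it through.** **Inputs from the protocol (Section 5).** Prevalence 2%, precision ±1 percentage point, Z = 1.96. The plan's own figure reproduces: 1.96² × 0.02 × 0.98 / 0.01² = 752.95, so 753; 753 × 1.10 = 828.3, so 829 to screen. The protocol gives no expected sensitivity, specificity, substudy size or CTA uptake.

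**Assumptions.** True sensitivity (Se) and specificity (Sp) are varied over a range. All invited participants have CTA. If the same share of positives and controls declined at random, the expected raw figures would not change, but the counts would shrink.

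**Formulas**, with N = 753 and p = 0.02:
- TP = N·p·Se; FN = N·p·(1−Se); FP = N·(1−p)·(1−Sp); TN = N·(1−p)·Sp
- DUS-positives P = TP + FP; controls C = 2P; verified fraction of negatives f = C / (FN + TN)
- Raw sensitivity = TP / (TP + f·FN)
- Raw specificity = f·TN / (f·TN + FP), approximately 2 / (3 − PPV)

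**Main case, Se 60% and Sp 99%.** TP = 9.04, FN = 6.02, FP = 7.38, TN = 730.56. P = 16.4, C = 32.8, f = 32.8 / 736.6 = 0.045. Missed webs expected among controls: 0.045 × 6.02 = 0.27.
- Raw sensitivity = 9.04 / (9.04 + 0.27) = 97.1% (truth 60%)
- Raw specificity = 32.56 / (32.56 + 7.38) = 81.5% (truth 99%)

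**Range at 2% prevalence:**

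| True Se / Sp | Controls | Missed webs among controls | PPV | Raw Se | Raw Sp |
|---|---|---|---|---|---|
| 50% / 98% | 44.6 | 0.46 | 33.8% | 94.3% | 74.9% |
| 50% / 99% | 29.8 | 0.30 | 50.5% | 96.1% | 80.0% |
| 70% / 98% | 50.6 | 0.31 | 41.7% | 97.1% | 77.3% |
| 90% / 99% | 41.9 | 0.09 | 64.7% | 99.4% | 85.0% |
| 50% / 99.9% | 16.5 | 0.17 | 91.1% | 97.8% | 95.7% |
| 95% / 100% | 28.6 | 0.03 | 100% | 99.8% | 100% |
| 50% / 95% | 88.9 | 0.94 | 16.9% | 88.9% | 70.4% |
| 20% / 95% | 79.8 | 1.35 | 7.5% | 69.1% | 68.0% |

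For Se 50-95% and Sp 98-100%, raw sensitivity stays between about 94% and 99.8%. The last two rows lie outside that range and show where the pattern weakens.

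**Does weighting rescue it?** Weight each verified control by 1/f. In the main case that is 736.6 / 32.8 = 22.4.
- Probability of no missed web among the controls: (1 − 6.02/736.6)^32.8 ≈ 76%. Weighted sensitivity is then 100%.
- With exactly one missed web: 9.04 / (9.04 + 22.4) ≈ 29%.

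Simulation (20,000 studies per scenario) at true Se 50% and Sp 99% gives a mean weighted specificity of 0.990, so specificity is repaired. Weighted sensitivity has mean 0.80, median 1.00 and a 95% range of 0.11 to 1.00; 74% of studies see no missed web. At true Se 90% and Sp 99% the 95% range is still 0.38 to 1.00. These simulations do not model the matching.

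**The case against.** Three readings go further than the documents allow.

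- **The bias occurs whatever the truth.** A reader might infer this, but it is not so. The specificity bias depends on PPV. It is about 2-4 points at true specificity 99.9% with sensitivity 50-95%, and nil at 100%. Raw sensitivity is not near 100% when true sensitivity is low and false positives are common (69% at Se 20% and Sp 95%).
- **The study will publish an unweighted table.** The protocol never says so. A separate analysis plan, not seen here, could specify verification weights. This narrows the criticism but does not remove it: the selection rule and the named outcome are protocol content, and correct weighting still leaves sensitivity almost uninformative.
- **The timetable makes adjudicated selection impossible.** Section 15 places "Central reads and adjudication" in May-June 2026 while scanning starts in January, and Section 10 allows 4 weeks for CTA. The start of that window is not stated, and the category calculated on the CRF (Section 7) could trigger the invitation. Impossibility is not shown.

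It is also fair to say that the substudy is optional, needs separate consent and does not enter the primary estimate, which is prevalence as seen on ultrasound. That lowers the severity. Some tempting remedies are weak too. Weights in each age-sex-site cell would rest on very few cases per cell. A prevalence corrected through the control CTAs would be unstable: one missed web among 33 controls would add about 1/33, or 3 percentage points, more than the whole assumed 2%. NPV from controls matched to the cases describes the cases' age, sex and site mix, not all DUS-negatives.

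**Conclusion.** The point stands as a mismatch between design and named outcome. Sampling on the DUS result supports PPV directly. It does not support sensitivity or specificity from the verified table, and no verification weighting is stated. Under 753 scans, 2% prevalence, full uptake and assumed Se 50-95% and Sp 98-100%, raw sensitivity would be about 94-99.8% almost independently of the truth. Raw specificity would fall short by an amount set by PPV, from nothing at Sp 100% to roughly 18 points in the main case. Weighting restores specificity. It does not make sensitivity usable with about 30-45 verified negatives (the number expected at Sp 99% and Se 50-95%).

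The Se and Sp values are assumptions, since the protocol gives none. This should be fixed before CTA invitations begin. It affects a secondary, optional result and leaves the primary prevalence estimate untouched.

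**What to change.** In Sections 10 and 11:

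1. Make PPV against CTA the target of the substudy.
2. Keep NPV as a secondary measure, either described as applying to the matched control distribution or weighted back to all DUS-negatives.
3. Report specificity only with verification weights, computed overall or in coarse strata.
4. Make no claim about sensitivity beyond a weighted estimate with its interval, labelled as imprecise.
5. Reconcile the categories invited to CTA (definite or possible) with the primary numerator (probable CaW), so that the PPV refers to the group counted in the primary outcome.

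The cost is mainly wording, plus any change in the number of CTA invitations that follows from reconciling the categories. The real loss is a headline sensitivity figure, which this sample could not have supported. If the sponsor wants to claim sensitivity, the number of verified DUS-negatives would need its own justification, with a larger random sample of them.

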1. Focal echogenic lesion in carotid bifurcation (15 mm proximally to flow divider and 15 mm distally)
2. The lesion is present (interferes) in the posterior wall
3. Echogenicity of the lesion is higher than intraluminal blood
4. Maximal length of lesions 3.0 mm
5. Minimal intraluminal prominence (width) 2.0 mm
6. In longitudinal view: Shape of lesion is shelf-like nor valve-like, triangular with the sharpest angle proximally with the blood flow direction
7. In transversal view: Transversal linear defect with echogenic surface projecting in the arterial lumen (the shape should be nest-like)
8. Hemodynamic signature: focal flow separation/recirculation or color aliasing immediately distal to the shelf without proportionate atherosclerotic plaque; spectral Doppler may be normal or show subtle focal acceleration without classic stenosis criteria.

Exclusion criteria:

1. The length is greater than the width
2. Visible only in transversal and not longitudinal view
3. Presence of carotid plaque (Mannheim consensus) in the posterior wall

Suspected carotid web:*Inclusion criteria:*

1. Focal echogenic lesion in carotid bifurcation (15 mm proximally to flow divider and 15 mm distally)
2. Minimal intraluminal prominence (width) 1.5 mm
3. One out of these criteria:
 - a. In longitudinal view: Shape of lesion is shelf-like nor valve-like, triangular with the sharpest angle proximally with the blood flow direction
 - b. In transversal view: Transversal linear defect with echogenic surface projecting in the arterial lumen (the shape should be nest-like)

Exclusion criteria:

1. Presence of carotid plaque (Mannheim consensus) in the posterior wall

Differential sonographic features to record: typical plaque (echogenic/heterogeneous with surface calcification), carotid diaphragm, dissection flap (mobile, intramural hematoma), carotid web with superimposed thrombus.

7) Sonographic Case Definition of Carotid Web

Required equipment/settings (if specified in your criteria):

- Probe / frequency: 5-14 MHz
- Settings: MI 1.6, 37 fps, Q scan, dynamic range 70
- Patient position: supine position, slight neck extension/contralateral head rotation

Diagnostic categories (tick all that apply):

- Definite CaW — must meet morphology, location, hemodynamics criteria and exclusions ruled out (plaque, dissection, diaphragm, artifact).
- Probable CaW — meets some morphology criteria and exclusions ruled out (plaque, dissection, diaphragm, artifact).

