- Not CaW — meets no criteria for CaW.

Morphologic measurements (standardized):

- Web thickness (mm): ____ (measured at ____)
- Web length/projection into lumen (mm): ____
- Projection angle (°) relative to vessel wall: ____
- Distance from flow divider (mm): ____
- Side: left / right / bilateral

Hemodynamic signatures (as per your thresholds):

- Color Doppler recirculation/aliasing: present / absent (criteria: ____)
- Spectral Doppler acceleration: PSV ____ m/s (cutoff: ____); ICA/CCA ratio cutoff: ____
- Microflow imaging pattern: ____

Differential exclusion checklist (define image features to rule out):

- Atherosclerotic plaque: ____
- Dissection flap/intramural hematoma: ____
- Carotid diaphragm/other membranes: ____
- Artifact (reverberation, blooming): ____

Image acquisition minimums (per side):

- Transverse cine (≥ 3 cycles) focused on bulb/ICA origin
- Longitudinal cine in ≥ 2 insonation planes (lat & post-lat)
- Still frames (B-mode \pm color) with calipers for all measurements
- Spectral Doppler waveforms (CCA, bulb, proximal ICA) with angle correction $\leq 60^\circ$

Quality grading (apply your rules):

- Grade 1 (excellent) / 2 (diagnostic) / 3 (limited) — use only Grades 1–2 in primary analysis; Grade 3 in sensitivity analysis.

Reader guidance & adjudication using your criteria:

- Two blinded readers score Definite/Probable/Possible/Not CaW; discrepancies resolved by third reader under the same rubric.

- 10% repeat reads for κ /ICC.

CRF add-ons (pre-wired to your criteria)

- Checkboxes for each criterion element (present/absent/not evaluable).
- Auto-calculated category (Definite/Probable/Possible/Not CaW) based on boxes ticked.
- Mandatory image IDs linked to each measurement.

8) Training, Blinding, and Adjudication

- Sonographers undergo a standardized training module with exemplar images and checklists.
- **Blinding:** Operators are blinded to participant clinical data except age/sex; central readers (two expert neurosonologists) are blinded to site and each other.
- **Adjudication:** Disagreements (probable/possible/absent) resolved by a third senior reader.
- **Reliability:** 10% random sample re-read for inter-observer agreement (Cohen's κ for categorical calls; ICC for continuous measures).

9) Data Collection

- **Demographics:** age, sex, ethnicity (optional), height/weight.

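### The primary numerator is contradictory: Section 11 counts Probable webs, and the protocol does not say whether Definite webs are among them

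*Protocol*

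**What the plan says.** Section 11 names the primary outcome as "Point prevalence of probable CaW" and adds a ratio in parentheses, "participants with ≥ 1 carotid web / all with diagnostic scans", which mentions no category. The first secondary outcome there adds Possible to Probable, and sensitivity analysis (i) in Section 12 likewise adds only Possible.

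The protocol has two sections numbered 7. The first gives criteria for a Definite web and for a second class, "Suspected carotid web". The second lists three categories. For Definite, a lesion "must meet morphology, location, hemodynamics criteria and exclusions ruled out". For Probable, it "meets some morphology criteria and exclusions ruled out (plaque, dissection, diaphragm, artifact". Not CaW is a lesion that meets none of the criteria.

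Further on in the second Section 7, "Two blinded readers score Definite/Probable/Possible/Not CaW", and the CRF calculates a category on the same four levels. Section 8 lists disagreements on a probable, possible and absent scale. Section 9 records "CaW category (absent/possible/probable". Section 10 invites "Participants with definite or possible CaW on DUS" and matched DUS-negative controls to CTA.

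**The concern.** This is the only primary quantity of a prevalence study, so its numerator has to be unambiguous. Central reads will arrive on a scale whose top level is Definite, while the primary outcome names the level beneath it. An analyst who follows the reader scale would leave the most certain webs out of the main result. An analyst who follows the data-collection scale would not. Both could cite the protocol.

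Two further consequences follow. The CTA substudy is meant to validate the DUS criteria, but it does not name the category that the primary outcome counts. And the 2% planning value in Section 5 is not tied to any category, so it is unclear which prevalence the study is sized to estimate.

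**Working it through.** **Step 1: the label sets, in reading order.**

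| Place in the protocol | Levels used |
|---|---|
| First Section 7 | Definite; Suspected |
| Second Section 7, diagnostic categories | Definite; Probable; Not CaW |
| Second Section 7, reader scoring and CRF auto-calculation | Definite; Probable; Possible; Not CaW |
| Sections 8 and 9 | probable; possible; absent |
| Section 10 | definite or possible; DUS-negative |

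That is five sets. Sections 11 and 12 then use probable and possible. No sentence maps one set to another.

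**Step 2: can the levels be matched by their criteria?**

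- Possible has no criteria anywhere.
- Suspected is not used as a category after its definition. Section 2 speaks of DUS-suspected webs, but as general wording.
- Suspected cannot simply be read as Probable. Suspected requires a bifurcation location, at least 1.5 mm prominence and one of two views, and excludes only posterior-wall plaque. Probable states no location or size requirement, but also excludes dissection, diaphragm and artifact.
- On the three-level list, a lesion that meets only the location or haemodynamic criteria is neither Probable nor Not CaW. On the four-level scale it might be Possible, but that level is undefined.

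**Step 3: the numerator under each scale.**

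- Four-level scale (readers and CRF): the primary outcome is Probable only, and the sensitivity analysis is Probable plus Possible. Definite is in neither.
- Three-level scale (Sections 8 and 9): Probable is the top level and may contain what Section 7 calls Definite.

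No listed prevalence outcome names Definite.

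**Step 4: possible size.** Inputs from Section 5: p = 0.02, d = 0.01, Z = 1.96.

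The plan's own figure reproduces: 1.96² × 0.02 × 0.98 / 0.01² = 752.95, rounded up to 753; 753 × 1.10 = 828.3, rounded up to 829.

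Expected carriers: 0.02 × 753 = 15.06, about 15. *Assumption:* these 15 are all the Definite plus Probable webs. The protocol gives no split, so the whole range from 0 to 15 Definite is open. With x Definite, the Probable-only prevalence is (15 − x)/753 and the shift is x/753. Intervals are Clopper–Pearson 95%, ignoring weights and clustering.

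| Definite (x) | Probable only | Prevalence (95% CI) | Shift, points |
|---|---|---|---|
| 0 | 15 | 1.99% (1.12 to 3.26) | 0 |
| 4 | 11 | 1.46% (0.73 to 2.60) | 0.53 |
| 8 | 7 | 0.93% (0.37 to 1.91) | 1.06 |
| 11 | 4 | 0.53% (0.14 to 1.35) | 1.46 |
| 15 | 0 | 0% (0 to 0.49) | 1.99 |

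At x = 7 the shift is 7/753 = 0.93 points, still inside the planned ±1 point. It first exceeds that target at x = 8.

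**The case against.** A reader might infer that the protocol plainly excludes Definite webs from its primary result. The text does not support that as the only reading, and it is probably not what was intended. Three points tell against it:

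- The ratio in Section 11 counts participants with at least one web, and the primary objective in Section 2 speaks of carotid web without a category.
- The category list in the second Section 7 allows more than one box to be ticked, and a Definite web would also meet some morphology criteria, so the levels could nest.
- Sections 8, 9, 11 and 12 use only probable and possible as positive labels. On that scale Probable is the top level, and adding Possible is a sensible sensitivity analysis. The second Section 7, where the four levels appear, still has blank cutoffs and template phrasing.

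These points stand as reasons to doubt the exclusion, but none settles it. The ratio conflicts with the label beside it. The readers' score and the CRF field appear to be one category per case, which does not fit nested levels. Nowhere does the protocol say that Probable includes Definite.

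A reader might also infer that the error must be at least as large as the planned precision. It need not be: with 7 or fewer Definite webs of 15 the shift is below 1 point, and with none it is zero.

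Finally, a statistical analysis plan may exist that names the levels. That would reduce the risk of a choice made after the counts are known, and nothing here shows that such a choice is intended. It would not remove the contradiction among the protocol's own case definition, reader scale, CRF field and primary outcome.

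**Conclusion.** The concern holds as a contradiction in the definition of the primary numerator, and it must be resolved. The protocol supports at least two numerators, Probable without Definite and Probable as a top level that contains Definite, and does not choose between them. The undefined Possible level carries the problem into the secondary prevalence outcome and sensitivity analysis (i), and Section 10 refers to a different pair of levels from the primary outcome.

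At the protocol's planning values the two readings could differ by anything from 0 to 1.99 percentage points. The difference exceeds the ±1 point target when 8 or more of about 15 carriers are Definite. This is an illustration: it rests on the 2% planning value covering Definite plus Probable together, and on a split that the protocol does not give. The sample size arithmetic itself is unaffected.

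**What to change.** 1. Adopt one ordered, mutually exclusive scale in Sections 7 to 12 and the CRFs, with written criteria for every level and a residual Not CaW level that takes everything else.
2. Merge the two Sections 7 and reconcile their exclusions. Adopting the first section's lists alone would lose the dissection, diaphragm and artifact exclusions, which stand as exclusions only in the second; these should be kept.
3. State the primary numerator cumulatively so that it always includes Definite webs: either Definite only, or Definite plus the next level. The choice is the sponsor's. The sensitivity numerator is then that set plus the next lower level.
4. Use the same labels in the Section 8 adjudication rule, the Section 9 field, the auto-calculated CRF category and Section 10, and say which level the 2% planning value refers to.

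Timing: make the change before scanning starts, which Section 15 puts in January 2026, or at the latest before any category counts are seen. Waiting for the central reads in May 2026 is too late, because the category is an ultrasound data field (Section 9, CRF-4) recorded during scanning, and the CTA invitations, with their 4-week window, depend on it.

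Cost: protocol wording and CRF relabelling only, with no extra participants or reads.
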